9.4 Quality Control of Interventions Administered

Quality control of the two interventions will be maintained through the following two procedures: 1) Interventions will be guided by detailed, written intervention manuals on which training and ongoing administration will be based; 2) Interventions will be audio-recorded and a random sample (approximately 10%) of the recordings across all sites will be reviewed by designated fidelity raters on a regular basis; adherence or deviation from a given intervention manual will be documented and discussed with the counselor during ongoing intervention fidelity meetings.

9.5 Concomitant Therapy

During part or all of participants' participation in the study, they may also be exposed to HIV street outreach, media campaigns, and/or other HIV prevention intervention. It would be both unethical and unfeasible to impede these activities. Therefore, to account for these activities, we will document them in the ACASI administered to study participants at the 6-month follow-up assessment interview. As part of the 6-month ACASI interview, we will ask participants if they have taken part in any HIV prevention discussions anywhere outside of this study.

10.0 STATISTICAL ANALYTIC PLAN

10.1 Objectives of the analysis

One primary hypothesis is proposed for this trial with the intention of testing whether 1) HIV rapid testing with brief prevention counseling and 2) HIV rapid testing with information only have different rates of incident STI at 6-month follow-up.

10.2 Randomization

Participants will be randomized to one of two treatment groups. Randomization will be stratified by site and within site, by race/ethnicity, gender and within males, by MSM versus heterosexual. The randomization procedure will be conducted in a centralized process through the Duke Clinical Research Institute (DCRI). Specifically, randomization schedules will be created by the study statistician for each randomization stratum within each site. The race/ethnicity categories will include: African American, Hispanic, European American, and other). Note that Hispanics of African origin will be classified as Hispanic for the purpose of randomization. The randomization schedules will be of a randomized-block nature to ensure relative equality of assignment across condition across the recruitment period and to prevent the potential for study staff quessing the next assignment which is heightened when a fixed block-size is used. After providing Informed Consent and subsequently completing the baseline assessment on ACASI and the STI testing, the site research coordinator (or designee) will perform the randomization. The research coordinator will contact the central randomization center to determine the appropriate condition for the site. The method of this notification will be by computer-assisted telephone. The research coordinator will enter the appropriate participant characteristics (site, participant ID, gender and ethnicity) by pushing appropriate telephone buttons. The treatment assignment will then be transmitted by computer voice (by telephone) and by fax or computer screen. The DCRI statistician will review the randomization data on a regular basis to ensure that the scheme is being implemented according to plan.

10.3 Primary Outcome

STI INCIDENCE: The primary outcome is composite STI incidence (Yes/No) at 6-month followup in which a person is considered positive for STIs if they are positive on any tested STI.

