4.0 STUDY AIMS AND HYPOTHESES

Primary Outcome

The primary outcome is composite STI incidence at 6-month follow-up in which a person is considered positive for STIs if they are positive on any tested STI.

Secondary Outcomes

Secondary outcomes include self-reported sexual risk behavior, being under the influence of substance and/or illicit drug use during sexual activity and cost and cost-effectiveness. The sexual risk and substance use behavior secondary outcomes will be measured at baseline and six months post-randomization as the self-reported number of unprotected sex acts (vaginal and/or anal sex without a condom) and sex while high on drugs or alcohol, which will be measured as the number of sexual occasions when substance use was involved. The cost analysis will consider the budgetary perspective of STD clinics, because decision makers in these programs may be unwilling to implement HIV counseling and testing unless they are reimbursed for costs according to their clinic's budgetary guidelines. The cost-effectiveness analysis will be conducted from the societal perspective (Hall et al., 2008), taking into account the time and expenses incurred by participants. Cost-effectiveness from payer perspectives will be considered in secondary analyses.

4.1 **Primary Aim and Hypothesis**

Aim 1: To determine the effectiveness of brief, participant-tailored prevention counseling in reducing STI incidence among patients seeking medical or health services at STD clinics

H1: The incidence of STIs among participants offered an HIV test with counseling will differ from participants offered an HIV test with information only.

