5.4.3 STI Testing

After giving informed consent, participants will be screened for a battery of STIs. MSM will be screened for rectal and urine Neisseria gonorrhea (GC), Chlamydia trachomatis (CT), Treponema pallidum (syphilis), and Herpes Simplex 2 (HSV-2). Women will be screened for vaginal GC and CT, Trichomonas vaginalis (TV), syphilis and HSV-2. Men who have sex with women will be screened for urine GC and CT, HSV-2 and syphilis. Gonorrhea and chlamydia will be measured by Gen-Probe Aptima combined nucleic acid amplification test (NAAT) which will be performed on urine, vaginal and rectal specimens. Trichomonas vaginalis will be measured by validated Gen-Probe Trichomoniasis Analyte Specific Reagent (ASR). All participants will have blood samples drawn to screen for syphilis and HSV-2. The diagnosis of syphilis will be determined by clinical history, positive non-treponemal (RPR or VDRL), followed by positive treponemal antigen tests (TPPA or FTA-ABS). We will use the Focus ELISA to assess HSV-2 seropositivity. The subset of positive HSV-2 samples will be confirmed via Western Blot (WB). This WB tests for HSV-2 and HSV-1 concurrently. Therefore, we will receive and provide both HSV-2 and HSV-1 results according to standard clinical guidelines and practice. While not part of our study outcome, we will analyze the HSV-1 results to understand HSV-2 and HSV-1 co-occurrence.

Specimens obtained for STI testing will be collected at baseline and 6-month follow-up, processed, and results will be recorded according to standard clinical guidelines and practice. Serum specimens obtained for HSV-2 testing will be collected at baseline and at 6 month follow-up. Specimens will be shipped to a central laboratory for initial storage and testing. In order to economize, the 6 month sample will be run first, if positive or indeterminate, the baseline sample will then be processed. If the 6 month sample is negative, the baseline sample will be discarded. In the event that a participant is lost to follow-up and does not return for the 6-month visit, we will process the baseline sample, as funding permits. Doing so will allow us to ascertain the baseline prevalence of HSV-2 among study participants. For women, the vaginal swab used for TV will be shipped to a central laboratory for processing and TV testing. TV specimens will be shipped and processed regularly so that results can be reported to each of the sites and appropriate patient follow-up can occur.

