10.5 Overview of Analysis Plan

The primary outcome will be analyzed using logistic regression for the binary outcome, new diagnoses of STIs (Yes/No). The logistic regression analysis will predict 6-month STI incidence as a function of randomization group controlling for the baseline incidence of STI. The test of the

hypothesis will be based on a likelihood ratio test comparing the model with and without the indicator for randomization group.

ANCOVA will be used for the secondary continuous outcomes, number of sexual risk behaviors and number of sexual episodes involving substance use. For example, the number of sexual risk behaviors at 6 months will be the outcome and the level of sexual risk behaviors at the baseline assessment will be the only covariate. The STI outcome, the test of the hypothesis will be based on an ANCOVA type specification test comparing models with and without the randomization group indicator. Costs will be compared based on study records supplemented by site-level data collection as described above. All analyses will be performed under intent-to treat (ITT) criteria.

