10.6 Statistical Power and Sample Size Calculation

All power calculations assume that the Type I error rate, α , is .05. Power calculations for main effects for treatment were made with PASS 2005. Power for interaction effects was calculated using a simulation program written in SAS 9.1.3. The original RESPECT study showed a significant effect of 6-month rate of new STIs which were 7.2% in the counseling arm and 10.4% in the didactic arm, for a difference of 3.2%. Though underpowered to be definitive, subgroup analysis of RESPECT-2 suggested that there is a differential effect of counseling on MSM compared to heterosexuals.

We therefore decided to power this study both to uncover a risk difference of 3.2% (with a higher base rate of STI incidence of 12.0%) and to have sufficient power to test for an interaction between MSM and non-MSM in which the ratio of risk ratios was approximately 2.0. Simulations showed that to have over 80% power for both the 3.2% risk difference overall and a 2 fold risk ratio interaction between MSM and other study participants required 1663 per group or 3326 total sample at the six month assessment. Although we anticipate closer to 85% follow-up, we used the conservative assumption of 70% retention for calculation of power. With the assumption of 70% retention, this means that 5000 must be randomized. Simulations assumed that 1/3 of the participants were MSM. Power for other, separate sub-group comparisons should be similar to that described above for MSM vs. non-MSM as long as the smaller subgroup in the comparison approaches or exceeds a third of the sample composition, which is consistent with the data we have obtained from the sites. For the secondary hypotheses of sexual risk behavior and substance use during sex there will be over 80% power to uncover a standardized difference between groups of .10, which is considered a small effect.

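### The primary-outcome sentence scores any positive test at 6 months and does not exclude infections present at baseline, so read literally it contradicts the plan's own incidence outcome, chiefly for HSV-2

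*Protocol*

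**What the plan says.** The event rule appears three times: in the Outcomes paragraph of the synopsis (section 2.0), in section 4.0 and in section 10.3. Each labels the outcome composite STI incidence at 6 months and then gives a single operational rule, "in which a person is considered positive for STIs if they are positive on any tested STI". None of the three refers to baseline status.

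Other sections describe a different quantity:

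- Section 10.1 states the hypothesis in terms of incident STI.
- Section 10.5: "The primary outcome will be analyzed using logistic regression for the binary outcome, new diagnoses of STIs (Yes/No"). The model adjusts for what it calls the baseline incidence of STI; the synopsis uses the same term.
- Section 10.6 takes its effect from an earlier trial's "6-month rate of new STIs which were 7.2% in the counseling arm and 10.4% in the didactic arm". It plans for a 3.2-point difference from a 12.0% base rate.
- Section 10.4.2 uses the primary outcome to estimate new STIs avoided, by type.

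Section 5.4.3 measures HSV-2 by antibody (ELISA, positives confirmed by Western blot). On the order of testing it says: "In order to economize, the 6 month sample will be run first, if positive or indeterminate, the baseline sample will then be processed". Syphilis is diagnosed from clinical history, a positive non-treponemal test and then a positive treponemal test.

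**The concern.** HSV-2 is assessed as seropositivity, and antibody from an infection acquired before randomization would normally still be present at 6 months. Under the stated rule such a participant is an event whatever the counseling does. The outcome then becomes 6-month positivity for HSV-2, while the hypothesis, the analysed variable and the sample size all refer to new infection.

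The label *incidence* does not settle the matter. The plan also applies that word to the baseline test, and a single baseline test can only show positivity. An analyst coding from section 10.3 could count prevalent HSV-2 and comply with the definition; one coding from section 10.5 would not count it. The two codings could give materially different event rates and power, and a null result under the first would be hard to interpret.

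**Working it through.** **Inputs from the protocol.** Section 10.6: two-group comparison, alpha 0.05, base rate 12.0%, difference 3.2 points (so 8.8% with counseling), 1663 per arm at 6 months, over 80% power, one third MSM. Section 4.1 states a non-directional hypothesis, so the test is taken as two-sided.

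**Assumed, because the protocol gives no value.** Baseline HSV-2 prevalence h of 10% to 50%; curable STI at baseline 15%; independence of these and of new infection; the same new-infection rate in all participants.

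**Step 1: reproduce the plan.** Power = Φ[(d√n − 1.96√(2p̄q̄)) / √(p₁q₁ + p₂q₂)], with d = 0.032, n = 1663 and p̄ = 0.104. This is Φ[(1.305 − 0.846)/0.431] = Φ(1.064) = 85.6%. For 80% power, 1428 per arm would suffice, so the MSM interaction sets the size. With assumed risk ratios of 0.44 (MSM) and 0.88 (others), interaction power at 1663 per arm is 80.9%. The stated figure of over 80% for both is reproduced when only new infections count.

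**Step 2: literal rule, no adjustment.** Event rate = h + (1 − h)p.

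| h | Information only | Counseling | Difference (points) | Power |
|---|---|---|---|---|
| 10% | 20.8% | 17.9% | 2.9 | 56% |
| 20% | 29.6% | 27.0% | 2.6 | 37% |
| 30% | 38.4% | 36.2% | 2.2 | 27% |

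**Step 3: why one composite baseline covariate does not repair it.** Take h = 20% and 15% curable STI.

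- The baseline-positive stratum is 0.20 + 0.80 × 0.15 = 32% of participants, and 0.20/0.32 = 62.5% of it are HSV-2 carriers.
- Its event rates are 0.625 + 0.375 × 0.12 = 67.0% and 0.625 + 0.375 × 0.088 = 65.8%, an odds ratio of about 0.95.
- In the baseline-negative stratum the rates are 12.0% and 8.8%, an odds ratio of about 0.71.

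The common odds ratio in the model averages the two and is pulled toward 1.

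**Step 4: literal rule with the planned logistic likelihood ratio test and that composite covariate.** Simulation at 1663 per arm, 4000 trials per setting:

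| Outcome counted | Power |
|---|---|
| New infections only | 85% |
| Literal rule, h = 10% | 63% |
| Literal rule, h = 20% | 53% |
| Literal rule, h = 30% | 44% |
| Literal rule, h = 40% | 38% |
| Literal rule, h = 50% | 32% |

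A repeat with 20,000 trials per setting gave 64%, 52%, 44%, 37% and 32%, so the differences are simulation error. With 20% curable STI at baseline instead of 15%, power at h = 10% to 40% was 60%, 48%, 41% and 33%.

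**Step 5: literal rule with HSV-2 status as its own covariate.** Carriers are then all events in both arms and carry no information, leaving 1663(1 − h) informative participants per arm: 1497, 1330 and 1164 at h = 10%, 20% and 30%. The Step 1 formula gives 82%, 77% and 72%.

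**Step 6: interaction.** On the literal rule, with the stratum risk ratios of Step 1 and no adjustment, interaction power falls from 81% to 43%, 27% and 19% at h = 10%, 20% and 30%.

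**The case against.** The strongest reply is that the disputed clause only says how components combine (any one is enough), and that the estimand is fixed elsewhere as incident or new infection. The testing order in section 5.4.3 supports this: if every 6-month HSV-2 positive were an event, there would be no need to run the stored baseline serum to classify it. Section 5.4.2 also links abstracted tests, results and treatments to evaluating the outcomes. As evidence of intent this is convincing, and it stands. It does not supply the rule: no section says that a baseline HSV-2 positive cannot be an HSV-2 event, or how an indeterminate pair is scored.

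A second reply is that scoring rules for each infection may sit in an SAP that is not shown. That is fair for the detail. But the protocol does state a rule, and an SAP that counted only new infections would depart from its wording.

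A reader might also infer more than the protocol supports:

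- *Old syphilis antibodies alone score as events.* They do not. Section 5.4.3 also requires clinical history and a positive non-treponemal test. Only a non-treponemal result that stays reactive is left unresolved.
- *Gonorrhea, chlamydia or trichomonas carried over from baseline is a large problem.* The synopsis plans on-site treatment of participants found infected, which limits this route.
- *Power is certain to collapse, or the 12.0% base rate cannot be met.* Both depend on literal application and on an HSV-2 prevalence the protocol never gives. Section 10.5 does not fix how the baseline covariate is coded, and Step 5 shows that this coding matters.

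**Conclusion.** The definition sentence in sections 2.0, 4.0 and 10.3 is wrong as written. It describes positivity at 6 months and conflicts with sections 10.1, 10.5 and 10.6. New infection is evidently what the trial means to count, and on that reading the sample size holds, with 85.6% power for the main effect.

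The power loss is conditional. On the literal rule with a composite baseline covariate, every assumed prevalence examined from 10% upward leaves power well below the 80% target. With a separate HSV-2 covariate, power stays near 80% at 10% prevalence and falls to 72% at 30%. The contradiction itself depends on none of these assumptions. Because it concerns the primary endpoint, it should be settled before any outcome data are seen.

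**What to change.** In sections 2.0, 4.0 and 10.3, define the event as at least one new infection since baseline, and add these scoring rules:

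- HSV-2 counts only when the confirmed 6-month sample is positive and the paired baseline sample is negative. State how a pair with an indeterminate result is scored.
- A syphilis serology already reactive at baseline is not by itself a new event.

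In section 10.5 and the synopsis Analysis paragraph, replace the term baseline incidence of STI with baseline STI positivity.

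The cost is protocol wording only. The baseline sera, the paired HSV-2 testing and the abstraction of tests and treatments are already planned in sections 5.4.2 and 5.4.3, and the sample size does not change.

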10.4 Secondary Outcomes

Secondary Outcomes will include sexual risk behavior, being under the influence of substances and/or illicit drug use during sexual activity and cost/cost-effectiveness. The sexual risk and substance use behavior secondary outcomes will be measured at baseline and six months post-randomization as the self-reported number of unprotected sex acts (vaginal or anal sex without a condom) and sex while high on drugs or alcohol, which will be measured as the number of sexual occasions when substance use was involved. The cost analysis will consider the budgetary perspective of STD clinics, because decision makers in these programs may be unwilling to implement HIV counseling and testing unless they are reimbursed for costs

according to their clinic's budgetary guidelines. The cost-effectiveness analysis will be conducted from the societal perspective (Hall et al., 2008), taking into account the time and expenses incurred by participants. Cost-effectiveness from payer perspectives will be considered in secondary analyses.

10.4.1 Risky Sexual Behavior Secondary Outcomes

The sexual risk behavior secondary outcomes are all continuous variables and are all self-reported. Examples of the secondary outcomes to be tested are:

a) Number of unprotected vaginal and anal sex acts with non-primary partners (all partners other than most recent primary) in the past six months

- b) Number of unprotected vaginal and anal sex acts with primary partner in the past six months
- c) Number of total vaginal or anal sex partners in the past six months
- d) Proportion of all vaginal and anal sex acts which involved drugs or alcohol in the past six months

10.4.2 Cost and Cost-effectiveness Secondary Outcomes

To determine staff and participant time delivering and receiving the Cost Measures: information or counseling session and testing, we will utilize data collected on case report forms that include start time and stop times. The self-reported session times will be independently validated when the study team fidelity raters review audio tapes representing approximately 10% of all sessions. We will use data collection tools that have been developed for a previous NIDA clinic trail (CTN 0032) to identify and measure the resources used for counseling training and quality assurance/fidelity assessment from study administrative records. During 1-2 day site visits, we will use structured interview guides adapted from guides used at CTN 0032 sites to collect data on site-level resources incurred for start-up activities, staff time that occurs outside of the intervention session but is directly related to the intervention, and overhead. To value personnel time, we will compare national average wage and fringe benefit rates to local wage and fringe benefit rates reported by the sites. The advantage of using national labor rates is that they provide a benchmark that can be adjusted uniformly to reflect different settings where the interventions might be implemented (Gold, Siegel, Russell, & Weinstein, 1996). Because some sites will use a staffing model in which HIV counseling and testing will be conducted by existing STD clinic staff members (not research staff), we assume that they can be deployed in other activities when not involved in implementing the intervention (i.e. no excess capacity). The cost of the rapid test will be the price paid by recipients of CDC funds for expanded rapid HIV testing. We will determine start-up costs, variable costs, and total costs (with overhead) by multiplying unit costs by the number of resource units consumed, and then calculate a cost per participant by study arm. Results will be reported as mean values and standard deviations, and differences between arms will be compared using chi-square and Fisher's exact test. Frequencies and percentages will be compared between sites and by individual cost element in order to identify outliers. Differences in costs by site and participant characteristics (e.g., age, gender) will be explored using multilevel modeling techniques. If we observe substantial skewness in specific costs, median values and inter-quartile ranges will be reported, and we will use Wilcoxon tests to compare medians and non-parametric bootstrap to compare means between study arms. We will also perform sensitivity analyses on costing assumptions that can vary by site location (e.g.

wage rates) or client volume (e.g., overhead).

Cost-Effectiveness: We will evaluate the cost-effectiveness of counseling and testing compared to information only and testing, by comparing the additional costs incurred in the counseling arm as described above with potential cost savings from the following sources: (1) avoided costs of treating STIs, (2) avoided costs incurred for individuals with untreated or ineffectively treated STIs, (3) avoidance of increased HIV transmission susceptibility with an STI and (4) lower HIV incidence due to risk behavior change. Table 2 summarizes this approach with representative data. STI treatment costs will be determined from the clinics and compared to published estimates, costs of complications of untreated STIs will be derived from the literature on the cost-effectiveness of STI screening, and data on HIV transmission risks will be from meta-analyses. We will use the results from the trial primary outcome to determine the impact of the counseling arm on reducing new STIs of each type, and multiply each of the STIs avoided by the weighted average cost of treated and untreated STIs (depending on the proportion likely to be treated in a non-research setting). This will provide us with an estimate of direct cost savings from the intervention. We will then consider the additional cost savings from avoiding HIV transmissions across a range of HIV incidence estimates, to determine the "threshold" incidence at which the intervention will be cost-saving. Secondary cases of STIs or HIV avoided among partners of the participants will not be considered in the primary analysis, but their impact can be estimated in a similar threshold analysis.

TABLE 2: STD Treatment Costs					
STD	Cost to treat (F=female, M=Male)	Long-term complications if untreated	HIV susceptibility multiplier		
Neisseria gonorrhea	\$37 (F), \$40 (M)	pelvic inflammatory disease, ectopic pregnancy, infertility, urethritis, epidymytis	2.1		
Chlamydia trachomatis	\$42 (F), \$45 (M)				
Syphilis	\$53	advanced disease**	2.2		
HSV-2	\$800 (F), \$450 (M)	relapse, maternal-fetal transmission	2.5		
Trichomonas vaginalis	\$46	preterm delivery	2.7		
HIV	\$303,100	advanced disease**	1.5		
*discounted lifetime cost from time of infection (Schackman et al. 2006) **maternal-fetal transmission is rare in the United States due to effective prenatal					
screening					

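### Section 10.4.2 names chi-square and Fisher's exact tests as the default comparison of mean cost per participant between arms; these are tests for categorical data and cannot test a difference in means

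*Protocol*

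**What the plan says.** Protocol sections 4.0 and 10.4 list cost and cost-effectiveness among the secondary outcomes. Under its cost measures, section 10.4.2 multiplies unit costs by the units of each resource used "and then calculate a cost per participant by study arm". The next sentence gives both the summary and the test: "Results will be reported as mean values and standard deviations, and differences between arms will be compared using chi-square" and Fisher's exact test.

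The rest of the paragraph adds three things:

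- A check on the data: "Frequencies and percentages will be compared between sites and by individual cost element in order to identify outliers".
- An exploratory model: "Differences in costs by site and participant characteristics (e.g., age, gender) will be explored using multilevel modeling techniques".
- A conditional alternative: "If we observe substantial skewness in specific costs, median values and inter-quartile ranges will be reported", in which case "we will use Wilcoxon tests to compare medians and non-parametric bootstrap to compare means between study arms".

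Section 10.5 refers back to this description for costs and names no other test. Its ANCOVA is assigned to the counts of sexual risk behaviors and of sexual episodes involving substance use, not to cost.

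**The concern.** The summary and the test in that one sentence do not belong together. A mean and a standard deviation describe a quantity measured on a continuous scale. Chi-square and Fisher's exact tests compare how counts fall into categories, and their null hypothesis concerns proportions. To apply them to dollar amounts, someone would have to choose cost bands after the fact, and the result would still say nothing direct about the difference in mean cost.

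This is not a detail left to a later statistical analysis plan. The protocol names a specific test, and the test is the wrong kind. If it is followed as written and costs are not judged substantially skewed, the formal between-arm comparison of a named secondary outcome is either impossible or rests on an unplanned banding of costs.

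**Working it through.** The protocol gives no power, effect size or numerical result for cost, so there is no figure to reproduce. The check has two parts: a reading of the text, and an illustration on assumed data.

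**1. Can the text be read so that the tests fit?**

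- The tests might have been meant for frequencies and percentages. Those come one sentence later and are compared between sites and by cost element, to look for outliers. They are not the comparison between arms.
- The multilevel models might be the real arm comparison. They are described as exploring cost by site and participant characteristics, not as the test of arm.
- Section 10.5 might supply another test. It does not; for costs it only points back.
- The bootstrap might be the intended default. It is introduced by the skewness condition, for which no threshold is given.

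No reading removes the mismatch when skewness is not judged substantial.

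**2. What do the named tests do with cost data?**

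Assumed inputs, none from the protocol: 500 participants per arm, normally distributed costs, standard deviation 15 dollars, control mean 50 dollars, true difference in means from 0 to 100 dollars.

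*Chi-square on the costs as they stand.* If all 1,000 values are distinct, the arm-by-value table has 1,000 columns with one person each. With equal arms, the expected count in every cell is 0.5, so each column contributes (1 − 0.5)²/0.5 + (0 − 0.5)²/0.5 = 0.5 + 0.5 = 1. The statistic is 1,000 × 1 = 1,000 on (2 − 1)(1,000 − 1) = 999 degrees of freedom, giving p = 0.485 whatever the means are. Welch's t-test on the same simulated data gives:

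| True difference (dollars) | Chi-square p | Welch t-test p |
|---|---|---|
| 0 | 0.485 | 0.55 |
| 1 | 0.485 | 0.0066 |
| 5 | 0.485 | 3 × 10⁻¹¹ |
| 20 | 0.485 | 8 × 10⁻⁶⁹ |
| 100 | 0.485 | 0 to machine precision |

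*Both tests after cutting costs into two bands.* A second assumed data set places 250 of 500 people above a 40-dollar cut in each arm, with the upper half costing about 60 dollars in one arm and about 120 dollars in the other. Chi-square and Fisher's exact tests both return p = 1.0. The arm means are about 35 and 65 dollars, and the t-test gives p of about 2 × 10⁻²⁶.

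The first case shows a test that cannot respond to the mean. The second shows one that answers a different question.

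**The case against.** The strongest reply is that this is a drafting slip of small consequence. Cost is a secondary outcome with no power statement attached in section 10.6, and the primary STI hypothesis, sample size and data collection do not depend on it. The same paragraph already names a sound method for means, and cost data are often skewed, so that method may well be the one used in practice. All of this stands. It bears on severity and leaves the mismatch in place.

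Four stronger readings are tempting, and the protocol does not support them.

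- A reader might infer that the cost-effectiveness analysis is undermined. That part of section 10.4.2 sets the additional cost in the counseling arm against potential savings and then looks for a threshold HIV incidence. It uses the estimated incremental cost, which comes from the arm means, and not the p-value of this test.
- A reader might infer that no valid test or interval for cost is available. The bootstrap of means is named for skewed costs. In addition, a large-sample interval follows from the means and standard deviations the plan will report: mean difference ± 1.96 × √(SD₁²/n₁ + SD₂²/n₂).
- A reader might object that the Wilcoxon test does not test mean cost. The protocol does not claim that it does: "we will use Wilcoxon tests to compare medians" gives it the medians, and the bootstrap is given the means.
- A reader might put a figure on lost efficiency by supposing a median split. The protocol proposes no split, so any such figure would describe an analysis that nobody has planned.

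**Conclusion.** The point holds in a narrow form. The default between-arm test for cost per participant does not match the quantity or its summary, and no other part of the protocol corrects it. The gap opens when skewness is not judged substantial, a judgement for which no threshold is stated. When skewness is judged substantial, the plan is sound for means.

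Severity is moderate to minor. One secondary outcome is affected, and only in its formal comparison. The estimate of incremental cost, the cost-effectiveness analysis built on it and the primary analysis are not affected. The conclusion rests on the wording of sections 10.4.2 and 10.5. The simulated figures only illustrate how the tests behave and are not estimates for this trial. A statistical analysis plan, which is not at hand, may already have corrected the test.

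**What to change.** Replace the test named in that sentence of section 10.4.2. Suggested content: the between-arm difference in mean cost per participant will be estimated with a 95% confidence interval by non-parametric bootstrap (or by a t-test or linear model); chi-square and Fisher's exact tests will be used only for categorical items reported as frequencies and percentages.

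If the bootstrap is chosen as the default, the comparison of means no longer depends on the skewness judgement. Medians, inter-quartile ranges and the Wilcoxon test can remain as supplements for skewed costs.

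The change is one sentence. It needs no additional data and has no effect on sample size or on any other analysis.
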